9.8 Parallel Qualitative Study

A patient may take part without their carers participation at any stage of this study. A carer may take part without the participation of the patient for the initial interviews/focus groups before stage 1 (pre-intervention) only. Separate information sheets and consent forms will be provided.

9.8.1 Qualitative Study Methodology

To ensure the proposed intervention and outcome measures are meaningful for people with brain tumours, we will undertake one-to-one interviews and/or focus groups. We have opted for both interviews and focus groups, where feasible, to offer participants choice and because both formats provide complementary but different data²¹. These will investigate both the experience of the intervention and suggestions for the recruitment, content and delivery format for an intervention. Interview schedules and topic guides will be drawn from PPI advice, the literature presented above and work from the Oliver Zangwill Centre on measuring patient-centred outcomes.

Participants will be approached to take part in the parallel qualitative study and information sheets provided by a member of the clinical care team. Initial agreement to be contacted about participating in interviews and focus groups will be obtained by a member of the clinical care team. This will include contact details of the potential participants to enable the qualitative researcher to discuss participation and obtain written informed consent.

A minimum recommended sample size for qualitative interviews with homogenous groups is 12 ²². Data collection will cease when data saturation is reached (defined as where no

information is generated to change or add to existing themes)22. Based on previous research, we expect data saturation with this sample size. Up to three focus groups may be run comprising 6-8 participants to enable people to feel comfortable to share their experiences focus discussion on the required topics²³.

A variation of methods will be used for the interviews and focus groups including: faceto-face, telephone or videoconference. If face-to-face method is used, focus groups will be run in three locations across East Anglia (Ipswich, Norwich and Cambridge) to ensure geographical location is not a barrier and reasonable travel expenses will be reimbursed; telephone and videoconference interviews can be completed to compensate for fatigue to meet current Trust Guidance for example during the COVID 19 pandemic. Interviews will last up to 60 minutes and focus groups up to 90 minutes depending on patient/carer preference, need for breaks and fatigue.

To ensure accuracy interviews and focus groups will be recorded and stored on an NHS shared drive accessible on an encrypted password protected NHS computer. Participants will be required to consent to this recording and will be instructed not to disclose personally identifiable information (such as their or other's names) but, if they do, these will be edited out (researchers to note if this occurs and the time on the recorder to facilitate edits). Recordings will be transcribed by the lead qualitative researcher who is an NHS clinical psychologist. Anonymised transcriptions of the interviews and focus groups may be shared with other researchers and anonymised direct quotes, from which participants cannot be identified, may be used in any scientific publications, presentations to clinicians, other scientists, the public or press. Recordings will be destroyed after the study results have been analysed. Anonymised transcripts will be kept and stored as part of the study data.

Interviews and focus groups with the research therapist and other staff involved in delivering the intervention will be performed in collaboration with our PPI advisors and supported by Brainstrust (https://brainstrust.org.uk) who have agreed to match the funding for these sessions. PPI advisors will provide service user representation and will be trained in the research method.

9.8.2 Timing of Focus Groups/Interviews

The focus groups/interviews will be undertaken at three stages of this project. Each will have specific objectives and aims:

- 1. Before start of study: we will involve patients that would be eligible to participate in stage 1 of the study and their carers. this group will explore the following topics:
 - a. What is the patient's and their family's lived experience of coping with disorders of social cognition?
 - b. What do the participants feel about the proposed study what potential barriers and enablers to trial participation can they see. This will be used to optimise the intervention before Stage 1.
- 2. After Stage 1: we will involve the patient group (including carer/family member) that had been recruited to Stage 1 of the study. We will explore:
 - a. Experiences of being involved in the study and study interventions?
 - b. How we may improve delivery of interventions and assessments?
 - c. How will we approach future patients to Stage 2 and discuss randomisation?
- 3. After Stage 2: we will involve the patient group (including carer/family member) that had been recruited to Stage 2 of the study. We will explore:

IRAS: 270758 SCARF-BT Protocol Version Number: 1.1

- a. How can we improve delivery of this intervention to routine clinical practice to make it acceptable to patients?
- b. What changes would we need to implement in a larger Phase III trial?
- c. How do the outcome measures reflect patient experience is there a discrepancy between changes in outcome measures and what patients experience?

9.8.3 Analysis

Data will be analysed via a qualitative method such as constant comparison analysis²⁴. The research team have expertise in developing interventions for people with neurological conditions and corresponding feasibility studies. An intervention will be developed based on knowledge from these prior interventions, and findings from interviews and focus groups with relevant stakeholders.

9.9 End of Study Participation

Patients will return to the normal standard of care once the Delayed Post-Operative Assessment is completed.

At the end of the study the patient and their family will be offered a final feedback session to explain the patient's problems and discuss possible strategies for dealing with these issues.

Participants will be offered a summary of the study findings.

9.10 Schedule of Assessments

Time Point	Study Screening		Baseline		INT-1	INT-2	INT-3	INT-4	INT-5	INT-6	INT-	INT-8	INT-9	Post -INT
Time Frame	<2 weeks post-op		<2 weeks post-op		Week 1	Week 1	Week 1	Week 2	Week 2	Week 2	Week 3	Week 3	Week 3	< 2 weeks before radiotherapy
Consent	Χ													
OCS-Bridge screening ¹	Х			Ra										
Medical History ²	Х	Re		and										
Clinical data ³	Х	Regist		lom										
DANVA2-AF ⁵			X	nisati										X
TASIT ⁶		ration	X	1 ti										X
TAS-20 ⁷		1 -	X	on ⁴										X
QoL questionnaire ⁸			Х											Х
Instruct patient9			X											X
INTERVENTION ¹⁰				1	Х	Х	Х	Х	Х	Х	Х	Х	Х	
Patient feedback ¹¹														X

- 1. Potential patients will be identified pre-operatively (as part of CogENT and SIND studies) for deficits using the OCS-Bridge screening tool., After consent, the OCS-Bridge screening tool will be used post-operatively during screening to ensure deficits remain
- 2. Medical history will include disease presentation, pre-existing neurological, psychiatric or hearing or visual problems that will prevent testing.
- 3. Clinical data will include performance status, histology of tumour, site of tumour.
- 4. Randomisation Stage 2 only
- 5. DANVA2-AF = Diagnostic Assessment of Non-verbal Accuracy-2, Adult Faces.
- 6. TASIT = The Assessment of Social Interference Test (Part 1)
- 7. TAS-20 = Toronto alexithymia scale.
- 8. Quality of life will be assessed using the EORTCQLQ-30 scale with the BN20 brain tumour module
- 9. Patients will be instructed to use the intervention a patient manual is available.
- 10. Intervention is either the Emotional Recognition Rehabilitation Intervention the Faces Intervention or General Cognition Control Intervention
- 11. A final patient feedback session will be offered to explain the patient's problems and strategies for dealing with this

10 Assessment of Safety

10.1 Definitions

10.1.1 Adverse Event (AE)

Any untoward medical occurrence in a patient or clinical trial which does not necessarily have a causal relationship with the study procedure.

An adverse event can therefore be any unfavourable and unintended sign (including an abnormal laboratory finding), symptom, or disease temporarily associated with study procedures, whether or not considered related to the study procedure.

10.1.2 Serious Adverse event (SAE)

Any untoward medical occurrence that:

- Results in death
- Is life-threatening
- Requires hospitalisation or prolongation of existing hospitalisation
- Results in persistent or significant disability or incapacity
- Consists of a congenital anomaly or birth defect; or
- Is otherwise considered medically significant by the investigator Some medical events may jeopardise the subject or may require an intervention to prevent one of the above characteristics/ consequences. Such events (hereinafter referred to as 'important medical events') should also be considered as 'serious'.

Life-threatening in the definition of a serious adverse event refers to an event in which the subject was at risk of death at the time of event; it does not refer to an event which hypothetically might have caused death if it were more severe.

10.2 Expected Adverse Events for this study

We do not expect any adverse events related to the study assessments or interventions.

10.3 Evaluation of Adverse Events

Only Serious Adverse Events (SAEs) as defined in section 10.1.2 that are suspected to be related to study procedures will be collected.

10.3.1 Assessment of seriousness

Seriousness is assessed against the criteria in section 10.1. This defines whether the event is an adverse event or a serious adverse event.

10.3.2 Assessment of causality

Definitely: A causal relationship is clinically/biologically certain.

Probable: A causal relationship is clinically / biologically highly plausible and there is a plausible time sequence between onset of the AE and study procedures and there is a reasonable response on withdrawal.

Possible: A causal relationship is clinically / biologically plausible and there is a plausible time sequence between onset of the AE and study procedures.

Unlikely: A causal relation is improbable and another documented cause of the AE is most plausible. Unrelated: A causal relationship can be definitely excluded and another documented cause of the AE is most plausible.

Unlikely and Unrelated causalities are considered NOT to be related to study procedures

SCARF-BT Protocol IRAS: 270758 Version Number: 1.1 Version Date: 18/03/2021

Definitely, Probable and Possible causalities are considered to be related to study procedures.

A pre-existing condition must not be reported as an SAE unless the condition worsens during the trial and meets the criteria for reporting or recording in the appropriate section of the CRF.

10.3.3 Assessment of severity

All SAEs experienced will be graded for severity according to the NCI CTCAE Toxicity Criteria (Version 4.03). CTCAE v4.03 can be downloaded from the following URL: http://ctep.cancer.gov/reporting/ctc.html

10.4 Reporting of SAEs

Only SAEs that are possibly, probably or definitely related to the study procedures will be recorded and reported.

The Principal Investigator needs to report all Serious Adverse Events which are **possibly**, **probably or definitely related** to the study procedures using the trial specific SAE form within 24 hours of their awareness of the event.

The Chief Investigator or his deputy is responsible for ensuring the assessment of all reported SAEs for expectedness and relatedness is completed and the onward notification of all related SAEs to the Sponsor immediately but not more than 24 hours of first notification.

If the SAE is deemed to be **related** and **unexpected** (i.e. not listed in section 10.2), it must be notified to the Research Ethics Committee within 15 days of first notification from the site using the Health Research Authority report of Serious Adverse Event form (see HRA website).

In the case of an SAE which is possibly, probably or definitely related to the study procedures, the subject must be followed-up until clinical recovery is complete and laboratory results have returned to normal or the disease has stabilised.

The completed SAE form can be emailed. Details of where to report the SAE's can be found on the front cover of the protocol.

11 Statistics

11.1 Number of patients

Up to 10 patients and their carers will be involved in interviews and/or focus groups prior to stage 1.

11.1.1 Stage 1

No formal sample size calculations were performed for Stage 1. Stage 1 will end either; when we understand the intervention and assessments are acceptable to patients and the technique is no longer evolving or; 10 patients have been recruited and undergone their final assessment - whichever is soonest.

Although we expect to screen more patients (up to a maximum of 20), we expect to recruit up to 10 patients to go forwards to the intervention at this stage.

SCARF-BT Protocol IRAS: 270758 Version Number: 1.1

11.1.2 Stage 2

For this study, our baseline scenario is where an uptake of above 50% or higher would seem acceptable while an uptake of the proposed intervention below 50% would be deemed unacceptable. With standard choices for significance level of 0.05 and a power of 80%, we would need a sample size of at least 19 subjects per arm to demonstrate feasibility

Acceptability/feasibility will be concluded if at least 50% of patients complete the proposed intervention. Assuming a significance level of 5%, 19 subjects in each arm would provide 80% power to observe at least 50% difference between the active FACES intervention and the control intervention.

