7.6 Study Outcome Measures

7.6.1 Stage 1: the cohort study

The specific outcome measures for this part of the study are:

- 1. Percentage of patients completing the intervention (defined as completing all 9 sessions).
- 2. Prospective recording of any changes to the administration, conduct and content of the rehabilitation intervention on a patient-by-patient basis.
- 3. The acceptability of the intervention will be explored through a parallel qualitative study (see below 7.6.3).
- 4. Percentage of patients completing the following validated outcome assessments
 - a. Diagnostic Assessment of Non-verbal Accuracy-2, Adult Faces (DANVA2-AF);
 - b. Emotion Recognition and Social Inference: The Awareness of Social Inference Test (TASIT), (part 1, EET subtest);
 - c. The Toronto Alexithymia Scale-20 (TAS-20).
- Percentage of patients and carers able to complete quality of life questionnaires.

7.6.2 Stage 2: placebo-controlled feasibility randomised controlled trial The outcome measures for this stage will be:

- 1. We will record the number of patients who undergo screening (the numerator) and the number of potentially eligible patients that attend clinic (the denominator). To proceed with a larger, efficacy study we would need to be able to use OCS-Bridge to screen a minimum of 75% of new patients.
- The percentage of screened patients meeting the eligibility criteria provide informed consent for the study. It will also be explored in more detail with the qualitative study (see below).
- 3. Percentage of patients who have completed all sessions for the FACES intervention (active intervention) and General Cognition Intervention (control intervention). To proceed to further studies this will again need to exceed 80%.
- 4. We will measure completion rates for the following established, validated outcome assessments pre- and post-intervention.
 - a. Diagnostic Assessment of Non-verbal Accuracy-2, Adult Faces (DANVA2-AF);
 - b. Part 1, which includes emotion recognition, of Emotion Recognition and Social Inference: The Awareness of Social Inference Test (TASIT);
 - c. The Toronto Alexithymia Scale-20 (TAS-20).

Acceptability will be explored with our parallel qualitative study.

- 5. Patient reported quality of life using the EORTC QLQ-30 with the BN20 brain tumour module¹⁹.
- 6. The impact of these problems on patient's families by asking interested family members to complete the Caregiver Quality of Life Index-Cancer (CQOLC).

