11.2.2 Stage 2 -Feasibility Assessments

- 1. To explore if we are able to screen patients with suspected high grade glioma attending clinic for deficits in emotional recognition. A deficit in emotional recognition is defined as scoring 11 or less on the emotional recognition test from the OCS-Bridge battery. To proceed with a larger, efficacy study we would need to be able to screen a minimum of 75% of new patients.
- 2. Acceptability will be assessed by calculating the percentage of screened patients that provided informed consent. The intervention will be considered feasible if at least 50% of patients meeting the eligibility criteria provided informed consent. This will be explored in more detail with the parallel qualitative study.
- 3. To Assess the compliance of the intervention and control arms, the percentage of patients who have completed all sessions will be calculated. Compliance will be concluded if at least 80% of patients complete all sessions.
- 4. Assess the acceptibility of the following established, validated outcome measures:
 - a. Diagnostic Assessment of Non-verbal Accuracy-2, Adult Faces (DANVA2-AF);
 - b. Part 1, which includes emotion recognition, of Emotion Recognition and Social Inference: The Awareness of Social Inference Test (TASIT);

IRAS: 270758 SCARF-BT Protocol Version Number: 1.1 c. The Toronto Alexithymia Scale-20 (TAS-20).

For each of these measures we will measure completion rates pre- and post-intervention. Acceptability will be explored further with our parrallel qualitative study.

- 5. To Assess the effect size of the intervention we will be assess changes in assessment measures (below) between the active (FACES) intervention group and the control group. Differences in scores will be assessed for:
 - a. DANVA 2-AF
 - b. TASIT using the TASIT version B at retest.
 - c. TAS-20 alexithymia.
 - d. QLQ30 and BN20 quality of life measures will be assessed using published minimal clinically important differences²⁵.
- 6. The difference between the Intervention group and the control group in Outcome Measures will be calculated together with 95% confidence interval. This will provide an early indicator that the intervention may make some difference and would be worth exploring in a larger, multicentre study as well as determining future sample sizes.

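### Stage 2 completion of the intervention is judged at 50% in section 11.1.2 and at 80% in sections 7.6.2 and 11.2.2, and the protocol never says how the two marks relate

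*Protocol*

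**What the plan says.** Four parts of the protocol bear on this.

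- **Section 11.1.2 (Stage 2 sample size).** It first says that "an uptake of the proposed intervention below 50% would be deemed unacceptable", then gives the rule "Acceptability/feasibility will be concluded if at least 50% of patients complete the proposed intervention". It does not say whether this covers the FACES arm only or both arms.
- **Section 11.2.2 item 3 (Stage 2 feasibility assessments).** For the intervention and control arms: "Compliance will be concluded if at least 80% of patients complete all sessions".
- **Section 7.6.2 item 3 (Stage 2 outcome measures).** The outcome is "Percentage of patients who have completed all sessions for the FACES intervention (active intervention) and General Cognition Intervention (control intervention"), followed by "To proceed to further studies this will again need to exceed 80" per cent.
- **Section 11.2.1 (Stage 1 stop/go).** Four percentages, one of them completion of FACES, are judged unacceptable below 50%, with a reference back to the sample-size section.

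A separate 50% mark in section 11.2.2 item 2 concerns consent: "The intervention will be considered feasible if at least 50% of patients meeting the eligibility criteria provided informed consent".

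**The concern.** Sections 11.1.2, 11.2.2 item 3 and 7.6.2 item 3 all set a rule for the same Stage 2 quantity, the share of patients who finish the intervention. The first is met at 50%; the other two need 80%. The labels differ (acceptability/feasibility, compliance, proceeding to further studies), but no text explains that they are levels of one scale.

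The study exists to answer feasibility questions, so a sentence that fixes when feasibility is concluded governs a headline result. For a completion rate from 50% up to just under 80%, the final report could declare the intervention feasible on section 11.1.2 and record a failed completion criterion on the other two. How prominently each statement is made could then be settled after the rate is known, which is what a pre-stated criterion is meant to prevent.

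**Working it through.** **1. Is it the same quantity?** The Stage 1 outcome in section 7.6.1 reads "Percentage of patients completing the intervention (defined as completing all 9 sessions"). Both Stage 2 programmes are three one-hour sessions a week for three weeks, so 3 × 3 = 9 sessions. The protocol gives no other definition of completing the intervention. Completing the intervention (11.1.2) and completing all sessions (7.6.2, 11.2.2) are therefore the same measure.

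**2. Does the sample-size calculation explain the 50%?** Section 11.1.2 works "With standard choices for significance level of 0.05 and a power of 80" per cent and reaches 19 per arm for a difference of 50 percentage points between arms. It states neither the arm rates nor the test. Assume 25% against 75%, two-sided, with continuity correction:

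- Uncorrected: n = [1.96·√(2·0.5·0.5) + 0.8416·√(0.25·0.75 + 0.75·0.25)]² / 0.5² = (1.386 + 0.515)² / 0.25 = 14.46, so 15.
- Corrected: n = (14.46/4)·[1 + √(1 + 4/(14.46·0.5))]² = 3.615 × 2.246² = 18.2, so 19.

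The planned 19 reproduces under these assumptions. It is a comparison between arms and tests neither completion mark.

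**3. Could 50% be the null value and 80% the target of a one-sample test?** The normal approximation at two-sided 5% and 80% power gives n = [(1.96·0.5 + 0.8416·√(0.8·0.2))/0.3]² = (1.3166/0.3)² = 19.3, so 20, which is close to 19. But the exact rejection rule with 19 patients would be at least 14 completers (one-sided 5%) or at least 15 (one-sided 2.5%). Neither is a mark in the protocol, and the protocol does not describe such a test.

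**4. Where do the marks disagree?**

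| Patients | 50% mark met from | 80% mark met from | Meets 50%, fails 80% |
|---|---|---|---|
| 19 | 0.5 × 19 = 9.5, so 10 | 0.8 × 19 = 15.2, so 16 | 10–15 (52.6–78.9%) |
| 38 | 0.5 × 38 = 19 | 0.8 × 38 = 30.4, so 31 | 19–30 (50.0–78.9%) |

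Exactly 80% cannot occur with 19 or 38 patients, so *exceed* (7.6.2) and *at least* (11.2.2) give the same result at these sizes.

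**5. How likely is a conflicting result?** With X binomial(n, p), the chance is P(X ≥ lower mark) − P(X ≥ upper mark). For n = 19 and p = 0.70 this is 0.967 − 0.133 = 0.834. The protocol gives no expected completion rate, so p is an assumption and a range is shown.

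| True completion | n=19: meets 50% | n=19: meets 80% | n=19: conflict | n=38: meets 50% | n=38: meets 80% | n=38: conflict |
|---|---|---|---|---|---|---|
| 60% | 0.814 | 0.023 | 0.791 | 0.922 | 0.004 | 0.918 |
| 65% | 0.913 | 0.059 | 0.853 | 0.981 | 0.020 | 0.960 |
| 70% | 0.967 | 0.133 | 0.834 | 0.997 | 0.079 | 0.918 |
| 75% | 0.991 | 0.263 | 0.728 | 1.000 | 0.231 | 0.768 |
| 80% | 0.998 | 0.455 | 0.543 | 1.000 | 0.500 | 0.500 |
| 85% | 1.000 | 0.684 | 0.316 | 1.000 | 0.799 | 0.201 |
| 90% | 1.000 | 0.885 | 0.115 | 1.000 | 0.968 | 0.032 |

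The conflict columns come from unrounded tails, so the last digit can differ from the difference of the columns shown.

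**The case against.** The strongest reply is that the progression rule is single. Only section 7.6.2 item 3 says what completion rate is needed before further studies, and section 11.2.2 item 3 agrees on 80%. Meeting a minimum for acceptability while missing the bar for a larger trial is not a logical contradiction. This stands in part. A reader might infer that the team could choose between 50% and 80% when deciding whether to go on; the protocol does not support that, because nowhere does it make 50% completion sufficient to proceed after Stage 2. The reply does not dispose of the point, because section 11.1.2 says that feasibility is concluded at 50%, not that 50% is a minimum, and no section sets out tiers.

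A reader might also infer that the 50% is the consent threshold of section 11.2.2 item 2, misplaced into a sentence about completion. Section 11.1.2 does speak of uptake, but section 11.2.1 relies on that section for a 50% floor on four quantities other than consent, including completion of FACES. That fits a general floor at least as well as a slip. It concerns Stage 1, however, and so does not reconcile the Stage 2 marks.

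Finally, the probabilities are large only if true completion lies inside or near the disputed band. That is correct: it would be wrong to call the conflicting results the most likely ones without stating the assumed rate.

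**Conclusion.** The inconsistency is real and should be fixed. For Stage 2, one section concludes feasibility at 50% completion, two others need 80% for the same quantity, and their relation is not stated. A result of 10–15 completers out of 19, or 19–30 out of 38, falls between the marks. The chance of that runs from 3% to 96% over true completion rates of 60–90% and the two denominators. It is most probable for rates of 60–75%, about even at 80%, and small only near 90%. These figures assume independent patients with a common completion rate, and the planned 19 per arm or 38 in total as denominator.

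The consequence is limited to what the report may conclude about feasibility. The 80% condition for proceeding, the treatment comparison and data collection are unaffected. That makes it a should-fix rather than a must-fix.

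**What to change.** Make one rule for Stage 2 completion, in either of two ways:

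1. In section 11.1.2, replace the 50% completion sentence with the 80% criterion already in sections 7.6.2 item 3 and 11.2.2 item 3.
2. Keep 50% in section 11.1.2, but state that it is only a floor (below it the intervention is not acceptable) and that 80% is required both to conclude compliance and to proceed.

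In either case:

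- Say whether the rule applies to each arm or to both together.
- Keep the 50% floor for the Stage 1 stop/go decision. If it leaves section 11.1.2, write it directly into section 11.2.1, which now borrows it from there.
- Keep the 50% consent mark of section 11.2.2 item 2. Restricting 50% to consent alone would leave the Stage 1 rule without its source.

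Using the same wording, *exceed* or *at least*, for the 80% mark is tidy but changes nothing at 19 or 38 patients.

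The cost is a few sentences of protocol text, with no added patients, assessments or data.
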